5.4 Demographics and baseline characteristics

Demographics and baseline characteristics will be analyzed as below.

- **Variables that will be presented by frequency and percentage**

Age group, concurrent disease, allergic history, period for infertility, causes for infertility*, previous ART experience, ART procedure*, levels of serum Luteinizing Hormone (LH), levels of serum Follicle Stimulating Hormone (FSH), previous treatments for infertility

* Multiple responses

- **Variables that will be presented by descriptive statistics (mean with standard deviation, median, minimum and maximum values)**

Age, period for infertility, previous ART experiences, serum Luteinizing Hormone (LH), serum Follicle Stimulating Hormone (FSH)

- **Variables that will be classified by ATC code**

- Previous treatments for infertility: The frequencies and percentages of subjects having previous treatments for infertility as well as previous treatments for infertility classified by ATC (Anatomical Therapeutic Chemical) code will be presented.

- Concomitant medication: The frequencies and percentages of subjects having concomitant medications as well as concomitant medications classified by ATC code will be presented.

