8. Applied SOPs.....	14

1. Objective of PMS

To analyze safety and efficacy information on Pergoveris™ in post-marketing uses, as well as factors likely to influence safety and efficacy

Primary objective: To get safety information in subjects using Pergoveris™

- 1) Serious Adverse Event (SAE)
 - ① If causing death or threatening one's life
 - ② If hospitalization or prolonged duration of hospitalization is necessary
 - ③ If causing continuous or significant disability or dysfunction
 - ④ If causing congenital malformation or abnormality
 - ⑤ Other medically critical conditions
- 2) Adverse event/adverse drug reaction unexpected in precautions
- 3) Already known adverse drug reaction
- 4) Non-serious adverse drug reaction
- 5) Other safety/efficacy related information (influence upon clinical laboratory value, etc.)

2. Patient population

Women with serious deficiency of Luteinizing Hormone (LH) and Follicle-Stimulating Hormone (FSH) at less than 1.2 IU/L of endogenous serum LH

3. Sample size

A total of 600 cases or more shall be reported as per the number of report cases pursuant to the Paragraph 3 of Article 6 of the 'Re-examination Standards for New Drugs Etc.' (Ministry of Food and Drug Safety Notification No. 2014-61).

4. Study items

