4.2 Medical history of subject

- 1) Concurrent disease
- 2) Allergic history

- 3) Period for infertility
- 4) Causes for infertility
 - ① Ovary factor
 - ② Cervical factor
 - ③ Uterine factor
 - ④ Oviduct factor
 - ⑤ Intra-abdominal abnormality
 - ⑥ Male infertility factor
 - ⑦ Immunological factor
 - ⑧ Unknown cause.
- 5) Previous ART experience
- 6) ART procedure
 - ① OI (Ovulation Induction)
 - ② IUI (Intra Uterine Insemination)
 - ③ IVF-ET (In Vitro Fertilization - Embryo Transfer)
 - ④ GIFT (Gamete Intra-Fallopian Transfer)
 - ⑤ ZIFT (Zygote Intra-Fallopian Transfer)
 - ⑥ ICSI (Intra Cytoplasmic Sperm Injection)
 - ⑦ Others

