5.7 Safety evaluation

- **Occurrence of adverse event**

- For adverse event (AE), adverse drug reaction (ADR), unexpected adverse event (UAE) and serious adverse event (SAE), the total number of subjects, the number of events, the occurrence rate and 95% confidence interval will be summarized.
- AE and ADR will be classified by the system-organ class (SOC) and preferred term (PT) using WHOART (WHO Adverse Reactions Terminology) for nth investigation report and MedDRA (Medical Dictionary for Regulatory Activities) for re-examination report, and summarized by the number of subjects, the occurrence rate and the number of events.
- The details of unexpected adverse event, serious adverse event and adverse event of subjects who are excluded from safety evaluation in accordance with paragraph 5.1.1 will be listed.
- Severity, causal relationship, actions taken regarding Pergoveris™ administration and progress of AE categorized by SOC and PT using WHOART for nth investigation report and MedDRA for re-examination report will be analyzed by presenting the number of events and

percentage. If there are several levels for severity, causal relationship, actions taken regarding Pergoveris™ administration and progress of the same AEs, the level that will be used for the analysis will be the worst one on subject level.

▪ **Factors that might affect the safety evaluation**

The occurrence of adverse event for each factor of demographics (age), baseline characteristics (concurrent disease, period for infertility, allergic history, previous assisted reproductive technology experience, luteinizing hormone, follicle stimulating hormone, previous treatments for infertility, concomitant medication), Pergoveris™ exposure (average daily dose, total duration, total dose) and special population (hepatic impairment, renal impairment) will be presented by the frequency and rate with 95% confidence interval. The AE rate for each factor will be analyzed using Pearson's chi-square test or Fisher's exact test.

Additionally, the occurrence of adverse event for all factors described above will be analyzed using multivariable logistic regression.

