5.8 Efficacy evaluation

▪ **Follicular growth and clinical pregnancy**

- Follicular growth: The frequency and percentage of subjects who are thought to be 'effective' (at least one follicle in more than 17mm of mean diameter on ultrasonography) will be presented.
- Clinical pregnancy: For the subjects who underwent clinical pregnancy test (urine HCG test or ultrasonography), the frequency and percentage of subjects who are pregnant (urine HCG test 'Positive' or ultrasonography 'Yes') will be presented.

▪ **Factors that might affect the effectiveness in follicular growth**

The effectiveness in follicular growth for each factor of demographics (age) and baseline characteristics (concurrent disease, period for infertility, allergic history, previous assisted reproductive technology experience, luteinizing hormone, follicle stimulating hormone, previous treatments for infertility, concomitant medication), Pergoveris™ exposure (average daily dose, total duration, total dose) and special population (hepatic impairment, renal impairment) will be presented by the frequency and percentage. The effective rate for each factor will be analyzed using Pearson's chi-square test or Fisher's exact test.

Additionally, the effectiveness for all factors described above will be analyzed using multivariable

logistic regression.

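### Causes of infertility and ART procedure are collected and tabulated, but they are the only two variables in the SAP 5.4 frequency list left out of the factor analyses in 5.7 and 5.8

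*SAP*

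**What the plan says.** SAP section 1 gives the purpose: to analyse safety and efficacy information "as well as factors likely to influence safety and efficacy".

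Section 4.2 collects "Causes for infertility" in eight categories, the first being an ovary factor. It also collects "ART procedure" in seven categories, from ovulation induction to ICSI and others. Section 5.4 reports both as frequencies and percentages ("causes for infertility*, previous ART experience, ART procedure") and marks both as allowing more than one answer.

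The safety factor analysis in 5.7 uses age, then "baseline characteristics (concurrent disease, period for infertility, allergic history, previous assisted reproductive technology experience, luteinizing hormone, follicle stimulating hormone, previous treatments for infertility, concomitant medication", then three exposure measures and hepatic and renal impairment. It adds that "the occurrence of adverse event for all factors described above will be analyzed using multivariable logistic regression". Section 5.8, under "Factors that might affect the effectiveness in follicular growth", uses the same list and the same kind of regression. Neither causes of infertility nor ART procedure appears in either section, and no reason is given.

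**The concern.** The lists in 5.7 and 5.8 take in nearly everything recorded at baseline, including allergic history. The efficacy endpoint is an ovarian response: at least one follicle above 17 mm in mean diameter. Whether a woman's infertility has an ovary factor is a natural candidate to influence that response, and the answer is already on the case report form. The type of procedure, if it is that of the treated cycle, could plausibly go with both the exposure given and the adverse events seen.

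Two things follow. The plan leaves part of its own question unasked. And because the regressions are confined to the listed factors, the estimated effects of daily dose, duration and total dose cannot be adjusted for either variable. If one of them is related to both exposure and outcome, an exposure difference could appear where there is none.

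**Working it through.** **Step 1. Compare the lists.** The ten variables in the 5.4 frequency list, against the factor lists:

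| 5.4 frequency list | In 5.7 | In 5.8 |
|---|---|---|
| Age group | yes (age) | yes (age) |
| Concurrent disease | yes | yes |
| Allergic history | yes | yes |
| Period of infertility | yes | yes |
| Causes of infertility | **no** | **no** |
| Previous ART experience | yes | yes |
| ART procedure | **no** | **no** |
| Serum LH | yes | yes |
| Serum FSH | yes | yes |
| Previous infertility treatment | yes | yes |

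Eight of ten are carried forward. Previous ART experience does not stand in for ART procedure, because 4.2 and 5.4 list them as separate items.

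**Step 2. How large could the confounding be?** The SAP gives no association of either variable with exposure or outcome, so every input here is assumed: a true exposure odds ratio of 1, 300 women in each exposure half (5.5 splits each exposure measure at its median; 600 is the minimum number of cases in section 3), and one omitted yes/no variable C.

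Let p0 be the outcome rate without C and p1 the rate with C, where odds(p1) = odds(p0) × OR_C. The rate in an exposure half is P(C) × p1 + (1 − P(C)) × p0.

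Worked case for follicular growth, with p0 = 0.70 and OR_C = 3:

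- odds(p1) = (0.70/0.30) × 3 = 7, so p1 = 0.875.
- Split 70/30: high half 0.7 × 0.875 + 0.3 × 0.70 = 0.8225; low half 0.3 × 0.875 + 0.7 × 0.70 = 0.7525. Crude OR = (0.8225/0.1775)/(0.7525/0.2475) = 1.52.
- Split 60/40: 0.805 against 0.770. Crude OR = (0.805/0.195)/(0.770/0.230) = 1.23.

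Over OR_C from 1.5 to 3, with p0 of 0.05 (adverse events) or 0.70 (follicular growth):

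| Split of C, high/low exposure | Spurious crude OR |
|---|---|
| 50/50 | 1.00 |
| 60/40 | 1.08 to 1.23 |
| 70/30 | about 1.17 to 1.52 |

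With OR_C = 1 the spurious OR is 1.00 whatever the split. If C lowers the outcome rate or goes with lower exposure, the bias runs the other way. In the strongest case (70/30, OR_C = 3), a two-sided 5% test with 300 per half would be falsely significant about 31% of the time at a 5% base adverse event rate, and about 55% at a 70% base growth rate.

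**Step 3. What would adding the variables cost the regression?** The present list has 1 (age) + 8 (baseline) + 3 (exposure) + 2 (special population) = 14 factors. Assume one parameter each and 600 women analysed. Events per parameter = 600 × rate / number of parameters:

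| Assumed AE rate | Events | 14 (as planned) | 15 (+ ovary factor) | 16 (+ grouped procedure) | 29 (+ all 8 + 7 indicators) |
|---|---|---|---|---|---|
| 5% | 30 | 2.1 | 2.0 | 1.9 | 1.0 |
| 10% | 60 | 4.3 | 4.0 | 3.8 | 2.1 |
| 20% | 120 | 8.6 | 8.0 | 7.5 | 4.1 |

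One or two collapsed terms cost little. Entering every category would roughly halve the events per parameter.

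**The case against.** Several points on the other side stand.

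- **ART procedure may not concern the treated cycle.** In 4.2 it is a medical-history item directly after previous ART experience, while current use of the drug has its own section (4.5). It may record the type of earlier procedures, and the SAP does not settle this. On that reading it does not reflect the current treatment plan, and part of its content is already covered by previous ART experience. The argument about causes of infertility does not depend on this.
- **Confounding is possible, not shown.** A reader might infer that the exposure effects are in fact confounded by two known determinants of outcome. The SAP gives no link between either variable and exposure or outcome, so it does not support that.
- **A striking illustration would mislead.** Suppose growth rates of 80% with and 95% without an ovary factor and a 70/30 exposure split. The halves then show 0.7 × 0.80 + 0.3 × 0.95 = 84.5% and 0.3 × 0.80 + 0.7 × 0.95 = 90.5%, an OR of (0.845/0.155)/(0.905/0.095) = 0.57. But that assumes a confounder with an odds ratio of (0.95/0.05)/(0.80/0.20) = 4.75. It is also a crude figure. The planned regression already includes age, LH, FSH, period of infertility and earlier treatment, and bias remaining after those has not been estimated.
- **The omitted items are the two that allow several answers.** Overlapping categories do not fit the single chi-square or Fisher comparison planned for each factor. That is a plausible, though unstated, reason for leaving them out. A yes/no coding removes the difficulty for the ovary factor.
- **Choice of covariates is partly judgement, and a protocol not seen here may bear on it.** Even so, 5.7 and 5.8 fix the lists themselves, and what they leave out sits badly with the aim in section 1.

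**Conclusion.** The omission is plain on the page. Both variables are collected and tabulated, both are absent from the factor tables and regressions in 5.7 and 5.8, and they are the only two in the 5.4 frequency list treated this way. The plan therefore does not examine two plausible factors, of which the ovary factor is the clearer case, and its exploratory exposure effects may be confounded by variables it cannot adjust for.

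The size is unknown. The odds ratios in the working rest wholly on assumed associations and are crude; they show what could happen, not what will.

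The reach is limited to the factor screening. The adverse event rates with their confidence intervals, which serve the primary safety objective, do not change, nor do the overall follicular-growth and pregnancy rates. This is a low-cost improvement to the plan, not a flaw in its main results.

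**What to change.** 1. Add ovary factor (yes/no) to the factor tables and regressions in 5.7 and 5.8. Code yes if that category is marked, alone or with others, and no if only other causes are marked. Treat a blank item as missing, in line with the no-imputation rule in 5.3.
2. State in 4.2 whether ART procedure records the treated cycle or earlier ones. If it is the treated cycle, add one grouped factor, for example IVF-ET, ICSI, GIFT or ZIFT against OI or IUI, with a rule fixed in advance for the others category and for women with answers in both groups. If it records earlier procedures, leave it as a descriptive item.
3. If either variable is to stay out, give the reason.

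No new data are needed. The cost is some SAP wording, extra table rows and one or two model terms; at an assumed 10% adverse event rate, events per parameter fall from 4.3 to 4.0 with one term or 3.8 with two. All 15 category indicators should not be entered. Whether the three overlapping exposure measures should all stay in the model is a separate question, and this change does not depend on it.

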5.5 Pergoveris™ exposure

Pergoveris™ exposure will be analyzed as below.

- **Administration period**

Administration period is defined as the sum of each administration period and will be summarized as descriptive statistics. Also, the administration period will be classified as two levels (\leq median, $>$ median) and presented by the frequency and percentage for each level.

- **Total dose**

Total dose is defined as the sum of total doses on each administration period and will be summarized as descriptive statistics. Also, the total dose will be classified as two levels (\leq median, $>$ median) and presented by the frequency and percentage for each level.

- **Average daily dose**

Average daily dose is defined as total dose divided by administration period and will be summarized as descriptive statistics. Also, the average daily dose will be classified as two levels (\leq median, $>$ median) and presented by the frequency and percentage for each level.

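### The univariate factor tests relate exposure to adverse events and follicular growth only through a sample-median split with no fixed cut-point, and the form of exposure in the logistic model is not stated

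*SAP*

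**What the plan says.** SAP section 5.5 gives each of three exposure measures two summaries. One is continuous; for daily dose, "Average daily dose is defined as total dose divided by administration period and will be summarized as descriptive statistics". The other is a grouping at or below versus above the median: "the administration period will be classified as two levels", "the total dose will be classified as two levels" and "the average daily dose will be classified as two levels". Section 5.5 gives no numeric cut-point and does not name the dataset or data cut that supplies the median.

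Section 5.7 lists "Pergoveris™ exposure (average daily dose, total duration, total dose" among the factors that may affect safety; I read total duration there as the administration period of 5.5. It presents the adverse event (AE) rate for each factor and adds: "The AE rate for each factor will be analyzed using Pearson's chi-square test or Fisher's exact test". Section 5.8 uses the same exposure factors for follicular growth: "The effective rate for each factor will be analyzed using Pearson's chi-square test or Fisher's exact test".

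Both sections then add a model. In 5.7: "Additionally, the occurrence of adverse event for all factors described above will be analyzed using multivariable logistic regression". Section 5.8 has the matching sentence for effectiveness. Neither says whether exposure enters that model as a continuous or a two-level term.

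**The concern.** Section 1 of the SAP makes it an aim to study factors likely to influence safety and efficacy, and exposure is an obvious candidate. Dose and duration are recorded as numbers, yet the univariate tests can use them only as categories, and the only categories defined in the text are the two sides of the sample median. Three things follow.

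- **Information.** All women on one side of the median are treated as equally exposed, so a graded relation is harder to detect.
- **Meaning of the groups.** The cut-point is not fixed, so high exposure has no set value. It could differ between reports. It could also differ between 5.7 and 5.8 within one report, because the efficacy dataset (5.1.2) is a subset of the safety dataset (5.1.1).
- **Ties.** Daily dose may cluster on a few values. Women at the median go to the lower group, so the upper group may be very small or empty.

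**Working it through.** **Inputs from the SAP.** Median split for all three measures (5.5); chi-square or Fisher for each factor (5.7, 5.8); 600 cases or more as a regulatory reporting number (section 3). The SAP states no power, effect size or exposure distribution, so it has no figure to reproduce.

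**Assumptions, not from the SAP.** Two-sided alpha of 0.05, an effect linear on the log-odds scale, and the distributions and AE rates below.

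**Step 1: information kept.** For a linear effect, the share kept is the squared correlation between exposure X and the indicator X > median. For a normal X this is 2/π = 0.637.

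- Loss: 1 − 0.637 = 0.363, about 36%.
- Effective number: 600 × 0.637 = 382.

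**Step 2: other shapes** (1,000,000 simulated values each).

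| Assumed exposure | Kept | Lost | Share above median |
|---|---|---|---|
| Uniform | 75% | 25% | 50% |
| Normal | 64% | 36% | 50% |
| Poisson, mean 8 days | 64.5% | 35.5% | 41% |
| Lognormal, log-SD 0.25 | 60% | 40% | 50% |
| Lognormal, log-SD 0.5 | 52% | 48% | 50% |
| Exponential | 48% | 52% | 50% |
| Three doses, 90/8/2% | 89% | 11% | 10% |
| Three doses, 30/50/20% | 62% | 38% | 20% |

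The range is about 11% to 52%. One case lies outside it: if more than half of the women share the highest dose used, the median equals that dose, nobody is above it, and the two-group test cannot be run.

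**Step 3: power, normal exposure.** Power after the split = Φ[(z₀.₉₇₅ + z_power) × √(2/π) − z₀.₉₇₅].

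- From 80%: (1.960 + 0.842) × 0.798 − 1.960 = 0.275, so Φ = 61%.
- From 90%: (1.960 + 1.282) × 0.798 − 1.960 = 0.626, so Φ = 73%.

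**Step 4: simulation check** (600 women, normal exposure, 4,000 runs, trend test against 2×2 chi-square). The log odds ratio per SD was set to (1.960 + 0.842)/√[600·p(1 − p)], aiming at 80% power for the continuous test.

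| AE rate p | Odds ratio per SD | Power, continuous | Power, split |
|---|---|---|---|
| 5% | 1.69 | 78% | 58% |
| 10% | 1.46 | 78% | 57% |
| 20% | 1.33 | 78% | 59% |

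**Step 5: how far an unfixed cut-point could move.** For a normal exposure, the standard error of the sample median is √(π/(2n)) SD: 0.125 SD at n = 100, 0.089 at n = 200 and 0.051 at n = 600. The two smaller sizes are assumed. With heavily tied doses the median may not move at all.

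**The case against.** The strongest reply is that a multivariable logistic regression is already planned for both outcomes, and nothing says that exposure is dichotomised in it. This stands. A reader might infer that the whole exposure analysis loses about a third of its information. The SAP does not support that: the loss is certain for the univariate tests and left open for the model. The silence is itself a gap, since the model takes the factors described just before it, and the only levels given for exposure are the two median groups.

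A second reply is that 5.5 uses the split only to describe exposure, so its use in 5.7 and 5.8 is inferred, and that the dummy tables are in an annex not shown, which might set other groups. The inference is reasonable, because the tests need categories and the text defines no others. Other groups would change the size of the loss.

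Third, a reader might infer that the median is recalculated at each report. The SAP does not say so. It mentions nth investigation reports and the re-examination report in connection with the coding dictionary, and does not say that the factor tests are repeated in each. What can be said is that the cut-point is not fixed. Within a single dataset the split is a well-defined contrast.

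Fourth, the power figures are illustrative. The simulated truth is log-linear, which favours the continuous term, and there is no power target to miss. This stands too. In addition, a continuous term does not cure near-absence of dose variation: with 90% of women on one dose, either analysis has little to work with, and Fisher's test already covers sparse cells.

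**Conclusion.** The point holds for the univariate exposure tests in 5.7 and 5.8. Under a linear effect and a roughly normal exposure, the split loses about 36% of the information, which would take 80% power to about 61%. The assumed shapes span about 11% to 52%, and the SAP gives no distribution from which to choose among them. It is established that the SAP leaves the cut-point and its source dataset unfixed and does not state the form of exposure in the logistic model. It is not established that the cut-point will move or that the model will use two levels.

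This is a worthwhile, inexpensive improvement and not a blocking defect. The factor analysis is exploratory, and the AE rates with confidence intervals that serve the primary objective are unaffected.

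**What to change.** - In 5.5, keep the median split for description only.
- In 5.7 and 5.8, assess exposure as a continuous term in logistic regression, both univariate and multivariable, reported as an odds ratio per fixed unit (for example, per day of administration), with a stated check of linearity on the log-odds scale.
- Enter one exposure measure at a time. Average daily dose is total dose divided by period, so on the log scale each measure is fixed by the other two. The sentence that puts all factors into one model needs rewording accordingly.
- If rates by exposure group are still shown, fix the cut-points and name the dataset they come from before the first report, and use the same values for the safety and efficacy sets.

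The cost is a few lines of SAP text and a changed model term; data collection does not change. The downside is the linearity assumption, which can be checked. If the true relation were a step near the median, the split would describe it better, so the result of the check should be reported.
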